6.5 Interim dose response modeling

MTD determination takes place at the end of the dose escalation phase and is based on the DLT rate during Cycle 1.

The following Bayesian dose-response analysis of the DLT rates will be performed during the interim reviews in order to guide the dose escalation decision.

Bayesian logistic regression

The analysis is based on a method reported by Tibaldi et al (3).

A range of doses will be tested, including possibly 100, 200, 300, 400, 500, 600, 700, 800, 900, 1000 and 1100 mg. Additional or alternative dose levels may be chosen. These possible dose levels are labeled as $d = 1, \dots, N$, where N is the maximum number of dose levels for the study. The probability, p , of observing a subject with DLTs during Cycle 1 is modeled as a function of dose:

$$\log\left(\frac{p}{1-p}\right) = \text{intercept} + \text{slope} * d$$

In this trial, the MTD is defined as the predicted dose where the DLT probability is 20%:

$$\text{MTD} = (\log(0.2/0.8) - \text{intercept}) / \text{slope}.$$

A Bayesian analysis will be performed, considering the following independent priors for the model parameters:

- intercept has a normal distribution with mean equal to -3 and variance equal to 1.
- slope has a positive normal distribution with mean equal to 0.0015 and variance equal to 0.003.

These priors were specified in the protocol. They are moderately-informative and were considered plausible in the context of the current dose escalation scheme and indication.

The posterior distribution of model parameters and the MTD will be estimated with the R package BRugs using MCMC techniques and considering at least 10000 simulations after convergence of the Markov chain.

The precision of the MTD will be monitored by calculating the relative median absolute difference (RMAD% = 100*mad/median). This robust estimator is a suitable statistic to quantify variability in asymmetric distributions. A low RMAD(MTD)% value indicates good precision.

In addition, the following posterior probabilities will be calculated for each dose level in the candidate set:

- T_d = (tolerable) Probability that the DLT rate is below 0.20, $\Pr(p < 0.20 | d)$, for a dose d .
- Q_d = Probability of dose d being the MTD. This is the probability that d is the maximum dose from the candidate set where $p < 20\%$.

Guidance for selection of next dose

The posterior density of the MTD and the Q_d probabilities in the candidate set are the two main instruments that will be reported to guide dose selection. They indicate on a continuous

Statistical Analysis Plan

Protocol No.: BAY 1163877/16443

Page: 19 of 20:

and discrete scale respectively the desirability for a dose to become the next choice. The larger the value, the more likely the corresponding dose is the MTD.

We recommended to compare the desirability of various dose candidates prior to making the dose selection decision. Doses with a high desirability are more likely to be the MTD, so they are preferred. When several doses have a similarly high desirability value, they are equally likely to become the MTD and the choice may be driven by other factors.

To avoid over dosing, only doses at most 2-fold larger than the maximum dose tested can be considered as candidates for the escalation process.

Guidance for stopping the dose escalation

Four indicators will be monitored and the dose escalation process may be terminated as soon as either statistic has reached a target threshold, as defined in the protocol.

1. MTD precisely estimated: CV(MTD) calculated as the inter-quartile range over the median is lower than 40%.
2. Maximum possible dose is safe $T_N > 80\%$.
3. Minimum dose tested (100 mg) is toxic ($T_1 < 20\%$).
4. Total sample size for next dose is already equal to 9.

Criteria 1. to 3. will end up in a conclusive dose escalation study. The conclusion will be either that 1. the MTD has been found, 2. all doses are safe or 3. they are all toxic. Criterion 4. does not lead to any interpretation about DLTs but it is a practical constraint to limit the overall duration of the study.

7. Document history and changes in the planned statistical analysis

- Approval of SAP, Version 1.0, 22 Mar 2018
- Approval of SAP Supplement, 11 Dec 2019
 - Added clarification regarding determination of MTD during the dose escalation part (section 3, section 51, section 6.5)
 - Update of treatment groups as specified in the TLF Specifications (section 4.2)
 - Deleted the statement on separate TLFs by study part (section 6)
 - Added population characteristics summaries for additional populations (section 6.1)
 - Added definition of all enrolled subjects (section 6.1.1)
 - Deleted overall survival and duration of stable disease as they are not efficacy endpoints in the protocol (section 6.2)

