6.4.2 Maximum tolerated dose

Individual listings of DLTs with CTCAE v4.03 code and grade will be presented.

The incidence of subjects with DLTs during Cycle 1 will be summarized by treatment and, if possible, modeled as a function of BAY 1163877 dose using Bayesian logistic regression. The moderately-informative independent priors used during the interim dose response analysis (see Section 6.5 for details) as well as non-informative priors will be used for this analysis to assess sensitivity of the estimates. Parameter estimates and model predictions will be reported with 90% credibility sets. The MTD will be computed as a derived function of model parameters as:

$$MTD = (\log(0.2/0.8) - \text{intercept})/\text{slope}.$$

The posterior distribution of the MTD will be summarized in tabular and graphical formats.

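### SAP section 6.5: the slope prior's variance does not fit its mean or the dose range, and d is used both as a level number and as a dose

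*SAP*

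**What the plan says.** Section 6.5 reads the same on this point in version 1.0 and in the 2019 supplement. It lists candidate daily doses, "including possibly 100, 200, 300, 400, 500, 600, 700, 800, 900, 1000 and 1100 mg", and numbers them d = 1 to N, "where N is the maximum number of dose levels for the study". The same d enters the model directly: logit(p) = intercept + slope × d. Yet p is said to depend on dose, T_d is defined for a dose d, and "the MTD is defined as the predicted dose where the DLT probability is 20" per cent.

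The priors are independent: "intercept has a normal distribution with mean equal to -3 and variance equal to 1", and "slope has a positive normal distribution with mean equal to 0.0015 and variance equal to 0.003". Of both, the SAP says: "They are moderately-informative and were considered plausible in the context of the current dose escalation scheme and indication".

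Two of the four stopping indicators are posterior probabilities from this model. Criterion 2 declares the maximum dose safe if T_N exceeds 80%. Criterion 3, "Minimum dose tested (100 mg) is toxic", applies if T_1 is below 20%. Section 6.4.2 plans the final MTD analysis with "The moderately-informative independent priors used during the interim dose response analysis" and, for sensitivity, with non-informative priors that have no numbers.

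**The concern.** A slope is defined per unit of d, so its prior means nothing until d has a unit. Section 6.5 gives d two meanings. The stated mean suits one of them (mg/day), and the stated variance suits neither.

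The model reports the candidate for the next dose, supplies stopping criteria 1 to 3, and is reused for the final MTD estimate, which serves a primary objective. A programmer who follows the text literally could code level numbers and obtain an MTD in levels. One who codes mg starts from a prior centred below the first dose given. The SAP reports no implied prior MTD or T_d that would have exposed either problem.

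**Working it through.** **Inputs.** From section 6.5: intercept ~ N(−3, variance 1); slope ~ N(0.0015, variance 0.003) restricted to positive values; target 0.20; 11 candidate doses from 100 to 1100 mg; cuts T_N > 80% and T_1 < 20%. From section 3: starting dose 100 mg/day. The SAP states no prior MTD or T_d, so there is no figure of its own to reproduce.

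**Slope prior.** SD = √0.003 = 0.0548, and 0.0548/0.0015 = 36.5. After truncation at zero the slope has median 0.0375 and mean 0.044, about 25 to 30 times the nominal 0.0015. The two figures cannot be moments after truncation either: that would need a coefficient of variation of 36.5, and a normal truncated to positive values has one below 1.

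**Prior means plugged in.** MTD = (log(0.2/0.8) − (−3))/0.0015 = (−1.386 + 3)/0.0015 = 1076. This lies inside the 100 to 1100 range only if d is in mg/day.

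**Whole prior.** MTD = (log 0.25 − intercept)/slope and T_d = Pr(intercept + slope × d < log 0.25), by grid integration and simulation, before any data:

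| Reading | Median MTD (quartiles) | T at lowest dose | T at highest listed dose |
|---|---|---|---|
| d in mg/day, variance 0.003 | 40 mg/day (19 to 90) | 0.23 | 0.02 |
| d in mg/day, SD 0.003 (assumption) | 568 mg/day (279 to 1205) | 0.90 | 0.27 |
| d as level 1 to 11, variance 0.003 | level 40 (19 to 90) | 0.94 | 0.855 |

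- First row: 77% of the prior mass for the MTD lies below 100 mg/day, and the prior median DLT probability at the starting dose is 69%. T_1 = 0.23 only just clears criterion 3's cut of 20%.
- Third row: the formula returns a level, not mg, and T_11 = 0.855 exceeds criterion 2's 80% with no patient treated. This depends on N: with 16 levels T_16 = 0.79, which does not.

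**Effect on early data.** After 0/3 DLTs at 100 mg/day (d in mg), the median MTD is 164 mg as written and 669 mg with SD 0.003. T at 200 mg is 0.42 and 0.89.

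**Effect on late data.** The doses are the escalation cohorts in section 4.1 of the supplement; the DLT counts are invented for illustration. With 0/3 at each of 100, 200, 400, 800 and 1200 mg/day and 2/9 at 1600 mg/day, the median MTD is 1782 mg as written and 1775 mg with SD 0.003. The interquartile range over the median, which is criterion 1's measure, is 0.63 and 0.61, so both give the same answer against 40%.

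**The case against.** The numbering d = 1 to N can be read as loose indexing, since the surrounding sentences speak of dose. That is the likelier intention, but the text still enters the index in the equation, so the unit needs stating.

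The model is also advisory. Section 4.4 says modelling may be done after selected cohorts, section 6.5 says escalation may be terminated, a 2-fold cap applies, and the sponsor decides with the investigators. This stands. It limits the consequence but does not make the prior right.

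The SAP attributes the priors to the protocol, which is not at hand, so the discrepancy may have begun there. The SAP nevertheless restates and endorses them.

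Several stronger inferences are tempting and not supported:

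- *That the final comparison with non-informative priors is empty.* The slope prior is nearly flat over the relevant range, but the N(−3, 1) intercept prior is not. In the late-data illustration, with the slope prior as written, an assumed vague intercept SD of 10 moves the median from 1782 to 1610 mg and the interquartile range over the median from 0.63 to 0.12. The contrast has content.
- *That on level numbers criterion 2 would stay met whatever the toxicity.* After 0/3 at levels 1, 2 and 4 and 2/6 at level 8, T_8 is 0.86, but criterion 2 uses T_N, and T_11 is 0.789: not met.
- *That the prior reverses the decision after 2/3 DLTs at 100 mg/day.* T_1 would be 0.04 as written and 0.47 with SD 0.003, but section 3 already restricts later cohorts to lower doses in that case, without the model.
- *That 0.003 is shown to be an SD.* A variance of 0.000003 would also give a plausible prior (median MTD 806 mg/day). The documents do not settle it.

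**Conclusion.** The specification is wrong as written. The stated mean and variance do not belong together on a mg/day scale, the unit of d is not fixed, and on neither reading does the prior match the SAP's own description of it. On the mg/day reading the prior median MTD is 40 mg/day against a 100 mg/day start. On the level reading criterion 2 is met before data, provided N is the 11 levels listed.

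The demonstrated effect is on early interim guidance, roughly a fourfold difference in median MTD after a first clean cohort (669/164 = 4.1). This rests on the assumption that the alternative is an SD of 0.003.

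A reader might infer that the final MTD estimate is materially distorted. The illustration does not support that between the two mg readings: they differ by 7 mg once data reach 1600 mg/day. It rests on invented DLT counts and does not cover a fit on level numbers, so the correction is still needed for the final analysis to be reproducible. This is a should-fix point, not one that invalidates the trial.

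**What to change.** - State in section 6.5 that d in the model is the total daily dose in mg, and use a separate index for the dose levels, including in T_1 and T_N.
- Reconcile the slope prior with the protocol and with the BRugs code actually run. Give SD, variance and BUGS precision together: variance 0.003 is precision 1/0.003 = 333; SD 0.003 is variance 0.000009 and precision 1/0.000009 = 111,111.
- If the printed variance is an error, correct it. If it was used as printed, remove the statement that the priors are moderately informative and plausible.
- Use the reconciled prior in the section 6.4.2 analysis, and give numeric values there for the non-informative intercept and slope priors.

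Cost: SAP wording and one re-run of a two-parameter model. No additional patients or data are needed.

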- The starting dose of BAY 1163877 is 50 mg given as a single dose on Cycle 1, Day 1, and twice daily (b.i.d.) from Cycle 1, Day 3 (100 mg / day).
- The maximum dose escalation will be 2-fold.
- Possible daily doses of BAY 1163877 starting from 100 mg in increments of 100 mg.
- The possible maximum dose of BAY 1163877 is considered to be 550 mg b.i.d. (1100 mg / day). Higher doses might be explored after discussions between sponsor and investigators.
- If at least 1 subject out of 3 or 1 out of 4 in a cohort has DLTs or if at least 2 subjects report drug-related AEs (CTCAE v4.03) of Grade ≥ 2 , any further dose escalation, de-escalation or cohort expansion will be decided in consultation between all investigator(s), and the sponsor (within the DSMT) after consideration of all available safety data of the previous cohorts. Any subsequent dose will be selected in order to determine the MTD.

Model-based dose-response analysis of the DLT rates will be performed during these interim reviews in order to guide the dose decision. The model-based dose selection procedure is considering data at all dose levels (not just at the last cohort). The dose predicted to yield 20% DLT rates will be reported from that model as a best candidate for the next cohort.

The final decision about the next dose will be made by the sponsor in consultation with all investigators (DSMT).

If the selected dose is larger than the last dose tested, then escalation will be pursued. If it is lower, a de-escalation step will occur.

Cohort expansion will occur when a previously tested dose is selected again for the next cohort of 3 subjects.

Expansions at any given dose up to a total of 9 subjects are allowed. In principle, the selection of a next dose level where the predicted DLT rate is close to 20% should insure that the next dose tested will remain safe.

Statistical Analysis Plan

Protocol No.: **BAY 1163877/16443**

Page: 10 of 20:

Nevertheless, the following constraint will be added in order to protect subject safety during the adaptive dose selection decisions:

- If 2 out of 3 (or 2 out of 4), at least 4 out of 6 (or at least 5 out of 9) subjects experience DLTs at a given dose level, only lower doses will be given in all subsequent cohorts because the probability that the dose is above the MTD is very large (above 95.4%).
- The dose-escalation procedure will be stopped as soon as:

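### In SAP section 6.5, Q_d for the top candidate dose is an open-ended tail probability, so it should not be ranked against the one-step Q_d of lower doses

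*SAP*

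**What the plan says.** Section 6.5 fits a two-parameter logistic model to Cycle 1 DLTs, with the slope constrained to be positive, and takes the MTD as the dose with a 20% DLT probability. For each candidate it calculates T_d, the probability that the DLT rate is below 20%, and Q_d, described as follows: "This is the probability that d is the maximum dose from the candidate set where" the DLT rate is under 20%.

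The guidance on the next dose names the posterior density of the MTD and the Q_d values as its two main instruments, one continuous and one discrete. It reads both as desirability: "The larger the value, the more likely the corresponding dose is the MTD", and then "Doses with a high desirability are more likely to be the MTD, so they are preferred". The top candidate gets no separate treatment.

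The dose list is not closed. Section 6.5 gives 100 to 1100 mg in 100 mg steps as possible levels and adds "Additional or alternative dose levels may be chosen". The escalation groups in section 4.1 of the 2019 supplement run to 1600 mg/day.

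Other rules bear on the choice. Section 3 (Determination of the MTD) says "The dose predicted to yield 20% DLT rates will be reported from that model as a best candidate for the next cohort". It also bars the current and higher doses from a stated number of DLTs: "If 2 out of 3 (or 2 out of 4), at least 4 out of 6" and so on. Section 6.5 limits escalation to a doubling. The sponsor decides with the investigators.

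**The concern.** A ranking by Q_d is fair only if each value measures the same kind of thing. A lower candidate is credited only with MTD values between itself and the next dose. The top candidate has no next dose, so it is credited with every MTD value above it, however far above. A large value there need not mean that the MTD is near that dose, although the guidance reads it so.

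What is at stake is the advice given straight after a first DLT in a first-in-human escalation. Q_d can then point to the highest dose on the list when the same posterior says that dose is probably too toxic, and when the companion MTD density points lower. The preferred dose can also change because the list was lengthened or shortened, with no change in the data.

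**Working it through.** **Inputs.** From section 6.5: logit(p) = intercept + slope × d; intercept N(−3, variance 1); slope normal with mean 0.0015 and variance 0.003, restricted to positive values; printed list 100–1100 mg in 100 mg steps. From section 4.1: levels 100, 200, 400, 800, 1200 and 1600 mg/day. Assumed: d is in mg/day, and the DLT counts, since the SAP gives none. The SAP prints no Q_d value, so there is no figure to reproduce.

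**Definitions.** T_d = P(intercept + slope × d < log 0.25) = P(MTD > d). Because p rises with dose:

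- below the top: Q_d = T_d − T_(next dose) = P(d < MTD ≤ next dose);
- at the top dose N: Q_N = T_N = P(MTD > dose N).

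This is algebra and needs no data.

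**Main example.** 0/3 at 100, 200 and 400 mg, then 1/3 at 800 mg; posterior by grid integration.

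- T_500 = 0.776 and T_600 = 0.625, so Q_500 = 0.776 − 0.625 = 0.151, the largest value below the top.
- Q_1100 = T_1100 = 0.232, so 1100 mg ranks first.
- P(DLT rate at 1100 mg ≥ 20%) = 1 − 0.232 = 0.77. The mean predicted DLT rate there is 47%.
- The median MTD is 694 mg. The MTD density peaks at 500–550 mg and at 1100 mg is 0.21 of its peak.

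**Moving the end of the list, same data, 100 mg steps.**

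| Last dose (mg) | Q of last dose | Q_500 | Ranked first (mg) |
|---|---|---|---|
| 900 | 0.323 | 0.151 | 900 |
| 1000 | 0.271 | 0.151 | 1000 |
| 1100 | 0.232 | 0.151 | 1100 |
| 1200 | 0.202 | 0.151 | 1200 |
| 1300 | 0.179 | 0.151 | 1300 |
| 1400 | 0.160 | 0.151 | 1400 |
| 1500 | 0.145 | 0.151 | 500 |
| 1600 | 0.132 | 0.151 | 500 |

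**Other first-DLT cases, two grids.** All lower section 4.1 levels are taken as 0/3. The 100 mg list ends at 1100 mg for a DLT at 800 mg and at 1600 mg for a DLT at 1200 mg.

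| First DLT | 100 mg grid: top Q against best lower Q | Section 4.1 levels: Q_1600 against best lower Q |
|---|---|---|
| 1/3 at 800 | 0.23 against 0.15: top leads | 0.13 against 0.51 (400 mg leads) |
| 1/4 at 800 | 0.30 against 0.13: top leads | 0.18 against 0.45 (400 mg leads) |
| 1/6 at 800 | 0.43 against 0.11: top leads | 0.26 against 0.32 (400 mg leads) |
| 1/3 at 1200 | 0.30 against 0.10: top leads | 0.30 against 0.34 (800 mg leads) |
| 1/4 at 1200 | 0.37 against 0.08: top leads | 0.37 against 0.32: top leads |
| 1/6 at 1200 | 0.49 against 0.07: top leads | 0.49 against 0.24: top leads |

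The grid matters because wider steps collect more mass. With 1/3 at 800 mg, Q_400 on the section 4.1 levels is T_400 − T_800 = 0.902 − 0.394 = 0.508.

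The effect is also absent for some data on the printed list: 2/6 at 800 mg ranks 500 mg first (0.19 against 0.14 at 1100 mg), and 1/3 at 400 mg ranks 200 mg first (0.28 against 0.09).

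**Prior check.** With slope SD 0.003 in place of variance 0.003, the top dose still leads in all six cases on the 100 mg grid (Q 0.28, 0.35, 0.46 and 0.30, 0.37, 0.49).

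**Do the stated limits act here?** The doubling cap allows 1100 mg after 800 mg (limit 1600) and 1600 mg after 1200 mg (limit 2400). The hard DLT constraint starts at 2 of 3. The SAP sets no minimum T_d for the next dose.

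**Would equal steps cure it?** Not alone. After 0/3 at 100, 200 and 400 mg with a list ending at 800 mg, Q_800 = 0.469. Cut to one step it is 0.047, and 300 mg leads at 0.115 after no DLT in nine subjects. In the main example the 1100 mg value becomes 0.030, but the tail above 1200 mg (0.202) still exceeds Q_500.

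**The case against.** The strongest reply is that Q_d is correct as defined. If the MTD lies above the list, the top candidate is the highest tolerable dose in the set, and any discrete probability depends on its grid. That stands. A reader might infer that Q_d is miscalculated; it is not. Only the reading of its size as desirability on a common scale fails.

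A reader might also infer that the plan would send the next cohort to the top dose. The SAP does not support that. It has no rule to take the largest Q_d. It reports the dose predicted to give a 20% DLT rate as a best candidate, calculates T_d for every candidate, and requires consultation after a DLT in 1 of 3 or 1 of 4 subjects. In the main example the median MTD of 694 mg is below the 800 mg just tested, so the other outputs point down.

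The size also depends on the grid: on the section 4.1 levels four of the six cases disappear, both 1/3 cases among them. Where the top dose still leads with 1/6 at 1200 mg, T_1600 is 0.49, so that dose is close to evenly balanced.

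Finally, the 2019 supplement lists escalation cohorts to 1600 mg/day and all expansion groups at that dose, and the MTD analysis in section 6.4.2 does not mention Q_d. These replies limit the weight of the point. They leave the guidance inaccurate at the end of the list, and nothing in section 6.5 warns of it.

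**Conclusion.** The point holds and is minor. That Q_N equals T_N follows from the SAP's own definition and positive slope. The advice to prefer larger values is therefore not like-for-like at the top dose and depends on a list end that the SAP leaves open. On the printed list it can put 1100 mg first (0.23 against 0.15) when that dose has a 77% probability of a DLT rate of at least 20%.

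The figures rest on doses in mg/day, the stated priors and assumed DLT counts. They show that the effect can occur, not how often it would. It is not evidence that any cohort was or would be overdosed: the output is advisory, other outputs contradict it in the main example, escalation appears complete, and no final estimate uses Q_d.

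**What to change.** In section 6.5:

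- State that for the top candidate Q_N = T_N = P(MTD above the top candidate). Report it on its own line and do not rank it against the other Q_d.
- Qualify the statement that a larger value means a more likely MTD, so that it excludes the top dose.
- Show T_d and the mean predicted DLT rate beside every Q_d.
- Base any choice of the top dose on T_N and on the dose predicted to give a 20% DLT rate, which section 3 already reports.
- Do not simply re-rank on equal 100 mg steps, because that can favour stepping down after no DLTs.

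The cost is a few sentences and a few lines of output code, with no extra data or patients. The drawback is that the top dose no longer has a rank value directly comparable with the others.
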